Research hypothesis	The level of MLR is related to the prognosis of patients with peritoneal dialysis. High levels of MLR may increase the risk of death, cardiovascular events and dialysis-associated peritonitis in patients with peritoneal dialysis.
Study Model	prospective cohort study

Sample size	
This study is based on a balanced control design of two groups to test whether there is a significant difference in survival rates. All-cause mortality and cardiovascular mortality are Primary Outcome Measures. Divided into high MLR group and low MLR group according to the median of monocyte / lymphocyte ratio (MLR). The previous research results show that the one-year survival rate of patients in the high MLR group was 86.6%, and the survival rate of patients in the low MLR group was 97%. Taking 0.05 as the statistical significance level on both sides, setting the test efficiency to 80%, adopting a 1: 1 balanced design, calculated by software PASS.11, it requires 84 cases in the high MLR group and 84 cases in the low MLR group. The one-year cardiovascular survival rate of patients in the high MLR group is 90.7%, and the cardiovascular survival rate of patients in the low MLR group 98.6%, taking 0.05 as the statistical significance level on both sides, setting the test efficiency to 80%, adopting a 1: 1 balanced design, calculated by software PASS.11, 127 cases are required in the high MLR group and 127 cases are in the low MLR group. Further assuming that the maximum rate of lost follow-up in each group will not exceed 5%, the final sample size is determined as 133 cases in the high MLR group and 133 cases in the low MLR group, for a total of 266 cases.

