
Statistical plan
	
Statistical hypothesis: test hypothesis H0: $\lambda 1 = \lambda 2$, that is, there is no difference in mortality and the Incidence of cardiovascular events between the high MLR group and the low MLR group.
 
Alternative hypothesis H1: $\lambda 1 \neq \lambda 2$, there is a statistical difference in mortality and the Incidence of cardiovascular events between the high MLR group and the low MLR group.
 
Main statistical analysis methods: Spss23.0 software was used for data statistical analysis. The continuity variables were tested for normality first. The continuous variables of normal distribution are represented by 'x \pm s'; the continuous variables of skew distribution are represented by median m; the data of classification or counting type are displayed by percentage. Two independent samples were used to compare the differences between groups in normal distribution measurement data, Mann Whitney U test was used to compare the differences between groups in non normal distribution measurement data, and chi square test was used to compare the differences between groups in classification or counting data. For missing values such as missing values and censored values, when the missing values are concentrated in a few variables and these variables are not the main variables for analysis, deletion can be considered, or the mean substitution method can be used to find alternative values for the missing values. The correlation between MLR and other indexes was analyzed by Spearman correlation and linear regression. Kaplan Meier curve was drawn to estimate the survival rate and cardiovascular disease incidence rate, and log rank test was used to check the difference. Single factor and multiple factor Cox regression models were used to explore the independent risk factors of death and cardiovascular disease in peritoneal dialysis patients, and to evaluate the correlation between MLR level and clinical all-cause and cardiovascular disease-related survival outcomes in peritoneal dialysis patients. Using HR risk ratio (95% CI confidence interval) to show the results, bilateral

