-------------------------	-------------------------------------------------------------------------------------------------------------------------------------------------------------------------------------------------------------------------------------------------------------------------------------------------------------------------------------------------------------------------------------------------------------------------------------------------------------------------------------------------------------------------------------------------------------------------------------------------------------------------------------------------------------------------------------------------------------------------------------------------------------------------------------------------------------------------------------------------------------------------------------------------------------------------------------------------------------------------------------------------------------------------------------------------------------------------------------------------------------------------------------------------------------------------------------------------------------------------------------------------------------------------------------------------------------------------------------------------------------------------------------------------------------------------------------------------------------------------------------------------------------------------------------------------------------------------------------------------------------------------------------------------------------------------------------------------------------------------------------------------------------------------------------------------------------------------------------------------------------------------------------------------------------------------------------------------------------------------------------------------------------------------------------------------------------------------------------------------------------------------------------------------------------------------------------------------------------------------------------------------------

	statistical standard p value < 0.05 has statistical significance.
--	-------------------------------------------------------------------

References

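### For cardiovascular mortality, take the Cox p-value and interval from the likelihood, not Wald statistics: a Wald result for high v low MLR would be significant in only about 65% of trials, while the planned log-rank test exceeds the stated 80%

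*Combined protocol and SAP*

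**What the plan says.** The Sample size section of the Summary table plans a two-group comparison of survival rates, with groups formed at the median MLR. All-cause and cardiovascular mortality are both primary outcomes. The design settings are: "Taking 0.05 as the statistical significance level on both sides, setting the test efficiency to 80%, adopting a 1: 1 balanced design". One-year cardiovascular survival is taken as 90.7% (high MLR) and 98.6% (low MLR), and the result is "127 cases are required in the high MLR group and 127 cases are in the low MLR group". An allowance of 5% for loss brings this to 133 per group, 266 in all. Cardiovascular mortality sets the size, since all-cause mortality is said to need only 84 per group.

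The Statistical plan section sets a null hypothesis of equal hazards in the high and low MLR groups and names the log-rank test for the difference between the Kaplan-Meier curves. It then gives univariable and multivariable Cox models two tasks: to look for independent risk factors, and "to evaluate the correlation between MLR level and clinical all-cause and cardiovascular disease-related survival outcomes in peritoneal dialysis patients". The closing sentence covers reporting and the threshold: "Using HR risk ratio (95% CI confidence interval) to show the results, bilateral" and "statistical standard p value < 0.05 has statistical significance".

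The plan names SPSS 23.0. It does not say whether the Cox p-value and interval are Wald, score or likelihood-based, and it does not say which result governs if the log-rank test and the Cox result disagree.

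**The concern.** The plan prescribes two analyses of the same primary outcome, a log-rank test and a Cox hazard ratio with its interval. With plenty of events in both groups they would nearly always agree. Here fewer than two cardiovascular deaths are expected in the low-MLR group. The log-rank test takes its variance under the null hypothesis and copes with that. A Wald test takes its standard error at the estimated hazard ratio, where it is dominated by the reciprocal of the very small low-group count, and it fails altogether when that count is zero.

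The stake is a paper in which the log-rank test is significant while the hazard ratio, which is what the plan says it will show, has an interval that includes 1 or no finite value. If the governing result is chosen only then, the choice is made with the data in view.

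**Working it through.** **Inputs (Summary table).** One-year cardiovascular survival 0.907 (high) and 0.986 (low), so event risks 0.093 and 0.014; two-sided 0.05; 80% power; 127 per group, 133 after 5% loss; one year of follow-up.

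**1. The plan's own figure.** Pooled two-proportion formula, with mean risk (0.093 + 0.014)/2 = 0.0535:

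n = [1.96 √(2 × 0.0535 × 0.9465) + 0.8416 √(0.093 × 0.907 + 0.014 × 0.986)]² / 0.079² = 126.2, rounded up to 127.

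Power at 127 is 80.3%. The plan's figure reproduces.

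**2. Implied hazard ratio and deaths.** With exponential survival, HR = ln 0.907 / ln 0.986 = 0.0976/0.0141 = 6.92. Expected deaths with 133 per group and no loss are 133 × 0.093 = 12.4 and 133 × 0.014 = 1.9. With 5% loss spread over the year they are about 12.1 and 1.8.

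**3. Chance of no low-group death.** 0.986^127 = 16.7%. At 133 per group with 5% loss it is about 16%. The Cox hazard ratio is then infinite and a Wald test cannot be significant.

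**4. Rough Wald power by formula.** At 127 per group, SE(ln HR) ≈ √(1/11.8 + 1/1.78) = 0.804; ln 6.92 / 0.804 = 2.41; power ≈ Φ(2.41 − 1.96) = 67%. This ignores the zero-death trials as such, so simulation is the better guide.

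**5. Simulation.** Exponential survival, censoring at one year, 5% exponential loss, 133 per group, the two median groups as the only covariate; 20,000 to 40,000 trials per run. Trials with no death in one group count as Wald non-significant.

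| Cardiovascular mortality | Significant |
|---|---|
| Log-rank | about 86% |
| Cox, likelihood ratio | about 88% |
| Cox, Wald | about 65% |
| HR not estimable (no low-group death) | about 16% |
| Wald, among estimable fits | about 77% |
| Likelihood ratio, among estimable fits | about 86% |

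The Wald figure is consistent with its parts: 0.84 × 0.77 = 65%. At 127 per group without loss, Wald power is about 63%.

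**6. Disagreement.** The log-rank test is significant and the Wald result is not in about 21% of trials: 16 points with no low-group death, and 5 points with a finite hazard ratio whose Wald interval includes 1.

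**7. Type I error.** With the mean risk of 5.35% in both groups (about 14 deaths in all), rejection rates are about 3% for Wald, 5% for log-rank and 5.5% to 5.8% for the likelihood ratio.

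**8. All-cause mortality (86.6% v 97%).** At the same size, Wald is about 86% and log-rank 89% to 90%. The problem is largely confined to cardiovascular mortality.

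**The case against.** A reader might infer that the plan makes the Cox hazard ratio its success criterion and that the real power is therefore 65% and not 80%. The documents do not support this. The sentence on the hazard ratio describes how results are shown, the 0.05 threshold is tied to no one test, and the test named for the group difference is the log-rank. The 80% belongs to the survival-rate comparison, where it is correct, and the log-rank test exceeds it. No printed figure is wrong.

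It is also fair to object that nothing in the documents says Wald. That is an assumption about how the Cox output will be read; the likelihood-ratio test from the same fitted model gives about 88%.

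Nor should the 65% be read as a general decline of the Wald statistic as the effect grows. With 12 high-group deaths, the mean Wald z is 2.20, 2.40 and 2.43 at three, two and one low-group deaths. Most of the shortfall is the zero-death trials, which would be visible as failed fits, and 16 of the 21 points of disagreement come from them. The loss with a finite hazard ratio is smaller but real: 77% against 86% for the likelihood ratio among estimable fits.

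Finally, the plan speaks of MLR level and of multivariable models, and the Follow up section averages repeated ratios. If MLR enters as a continuous variable, these figures do not apply.

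All of this limits the point without removing it. The plan does give Cox regression the task of evaluating MLR against cardiovascular survival, and only that model can address independent risk. It leaves the statistic unstated where the choice matters.

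**Conclusion.** The point holds as a cheap improvement to the analysis, not as an error in the stated power. If the Cox result for high v low MLR is read from Wald statistics, it will be significant in about 65% of trials at the plan's own rates, will be inestimable in about 16%, and will fail to support a significant log-rank test in about 21%. Likelihood-based inference from the same model brings the 65% to about 88%.

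This rests on four assumptions: Wald inference, median groups in the Cox model, exponential survival, and no covariates. Adding non-cardiovascular deaths at the rates implied by the all-cause figures changes the Wald figure only to about 64%. Covariate adjustment was not modelled, because the documents give no covariate effects.

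**What to change.** In the Statistical plan section:

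- Confirm that the log-rank test decides high v low MLR for cardiovascular mortality.
- For the Cox models, take the p-value for MLR from the change in −2 log-likelihood when MLR is added, and the 95% CI from the profile likelihood, in place of Wald statistics.
- When the low-MLR group has no cardiovascular deaths, report the hazard ratio as not estimable from above and give a one-sided lower bound from the profile likelihood.

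The Sample size section can keep its 80%; it would help to say that this is the power of the survival-rate comparison. If a Wald interval were to be decisive instead, about 160 to 165 evaluable patients per group would be needed for 80% (79% at 160, 84% at 175).

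The cost is two or three sentences and no extra patients or data. The profile-likelihood interval is likely to need a short script or another package beside SPSS. The likelihood-ratio test is slightly liberal at this event count, with a type I error of about 5.5% or a little more, and the plan should say so.
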